2.2 Sample size consideration

Sample size estimations have been made on the assumption that for a valid statistical data analysis according to Kaplan-Meier, at least 100 implants surviving 10 years are necessary. Over a period of 10 years, a drop-out rate of 30% should be considered. Therefore, 150 initial implantations are needed in each group.

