3 STUDY METHOD

3.1 General

Patients' pre-operative status, surgical procedure as well as clinical and radiological outcome will be documented by means of Case Report Forms (CRFs) that are provided by the study sponsor. CRFs will be filled in the investigator or specially assigned hospital personnel who have been trained for the study. Completed CRFs are faxed from the site to the sponsor immediately upon completion. Case Report Forms are the basis for further data evaluation.

Pain, function, gait, range of motion (HHS) and radiographic status determinations are made pre-operatively and at each post-operative examination. Radiographic analysis will be done on standard AP and lateral view X-rays.

Pre-and postoperative HOOS questionnaires are filled in by the patients themselves. Patients must have the possibility to complete the forms on their own, without any external influence. This means patients should have the possibility to take the questionnaire home and return it to the hospital at a later date.

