3.3 Follow-up

The follow-up schedule is shown in table 1.

Table 1: Time windows for investigations

	Time-window	HHS/HOOS	Clinical	Radiographic
Preoperative	45–0 days	X	X	-
3 months	10–14 weeks	X	X	X
1 year	11–13 months	X	X	X
3 years	36–38 months	X	X	X
5 years	60–63 months	X	X	X
10 years	120–123 months	X	X	X

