3.4 Complications/adverse events/lost-to follow-up

Complications and adverse events are noted at each follow-up interval. For completed observations due to death of the patient, explantation of the device or patient's address unknown the latest status will be recorded as an endpoint. Patients will be considered lost to follow-up after they have missed two visits and all attempts to locate and evaluate them have failed. Patients who refuse to attend follow-up or patients unable to attend follow-up will be assessed by telephone if possible. Minimal data concerning the implant status should be acquired by telephone.

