5.2 Secondary Endpoints

- Harris Hip Score (HHS)
- HOOS Score (Hip Dysfunction and Osteoarthritis Outcome Score), which includes the complete WOMAC Osteoarthritis Index
- Radiological: radiolucent lines, osteolysis, hypo- and hypertrophy of the cortex, loosening of the implant or migration

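### The protocol gives no way to obtain HOOS from patients who stop attending, so a missed 10-year score would be filled by a carried-forward one about five or more years old

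*Protocol*

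**What the plan says.** Protocol 3.4 keeps contact with non-attenders: "Patients who refuse to attend follow-up or patients unable to attend follow-up will be assessed by telephone if possible". It then sets the minimum content of that contact: "Minimal data concerning the implant status should be acquired by telephone". No other item is named. The same section has complications and adverse events noted at each follow-up interval.

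The protocol summary lists HOOS among the main study parameters, and Table 1 (Protocol 3.3) schedules it at every visit up to the 10-year window of "120–123 months". On how it is completed, Protocol 3.1 says "Pre-and postoperative HOOS questionnaires are filled in by the patients themselves" and adds that "patients should have the possibility to take the questionnaire home and return it to the hospital at a later date". The reason given is to keep the answers free of outside influence. Posting a form to someone who missed a visit is not mentioned in either document.

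The SAP places function and pain by HHS and HOOS under its primary objective (4.1) and lists the score as a secondary endpoint (5.2): "HOOS Score (Hip Dysfunction and Osteoarthritis Outcome Score), which includes the complete WOMAC Osteoarthritis Index". SAP 7.11 compares preoperative with postoperative scores by a paired test. SAP 7.3 fills missing outcome values at designated time points by last observation carried forward (LOCF).

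**The concern.** Contact with a non-attender is already planned, and the HOOS is one of the few outcomes that does not need an examination room. HHS range of motion and radiographs do need one. Followed to its stated minimum, however, a call to a willing patient yields a stem status and no HOOS.

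Patients who stop attending are unlikely to be a random sample. Some will be disabled or dissatisfied; others will be well and see no reason to come. The SAP then carries an old score forward, and it enters the 10-year comparison as if it were current. Late deterioration is what a 10-year study should be able to show, and a carried-forward value cannot show it. Complications are also absent from the stated telephone minimum, although postoperative adverse events to 10 years are a safety endpoint (SAP 5.4).

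**Working it through.** **The plan's own figure.** The only derivation in the documents is in Protocol 2.2: 100 implants at 10 years with 30% drop-out, giving 150. Direct inflation gives 100 / (1 − 0.30) = 142.9, so 143. The stated 150 is not reproduced exactly, but it errs on the safe side (150 × 0.70 = 105) and does not affect this point. Only the 30% is used below.

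**Inputs**
- Drop-out: "Over a period of 10 years, a drop-out rate of 30% should be considered" (Protocol 2.2).
- Patients: 225 enrolled and implanted (SAP 7.15).
- Visit windows: 36–38, 60–63 and 120–123 months (Protocol 3.3).
- Scale: 0 to 100 for each transformed WOMAC subdomain (SAP 7.4).
- Difference between non-attenders and attenders: not in the documents. Assumed d = 5 to 15 points, with non-attenders worse. If they are better, the sign reverses.
- Share of non-attenders who would return a form: not in the documents. Varied below.

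**Age of a carried-forward 10-year score**
- Last form at 5 years: 120 − 63 = 57 to 123 − 60 = 63 months, about 5 years.
- Last form at 3 years: 120 − 38 = 82 to 123 − 36 = 87 months, about 7 years.

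**Number affected.** 225 × 0.30 = 67.5 without a 10-year HOOS, leaving 157.5 with one. This reads the 30% as everyone without a 10-year visit, which is an assumption because the protocol does not define drop-out.

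**Error of an observed-case mean.** Let A be the attenders' mean.
- True mean: 0.70A + 0.30(A − d) = A − 0.30d.
- No forms recovered: the observed mean is A, so the error is 0.30d, that is 0.30 × 5 = 1.5 to 0.30 × 15 = 4.5 points.
- Half recovered and representative: the observed mean is A − (0.15/0.85)d. The error is (0.30 − 0.15/0.85)d = (0.30 − 0.1765)d = 0.124d, about 0.6 to 1.9 points.

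The recovered forms enlarge the denominator and also move the observed mean, so the remaining error is not simply 0.15d.

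**Precision.** The half-width of a 95% interval for a mean change, in SD units, is 1.96/√n.

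| Drop-outs returning a form | n | Half-width |
|---|---|---|
| 0% | 157.5 | 0.156 |
| 50% | 191.25 | 0.142 |
| 100% | 225 | 0.131 |

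The gain in precision is modest. Bias matters more.

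**Error under LOCF.** This is the share of patients filled multiplied by their mean change between the last form and 10 years. The documents give neither quantity, so no figure can be put on it.

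**The case against.** The text is less restrictive than it may look, and four stronger readings should be set aside.

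- *The call is limited to implant status.* Protocol 3.4 sets a floor. A telephone assessment leaves room for more, and the CRFs, which are not among the documents, may itemise it.
- *The protocol already allows HOOS without a visit.* Protocol 3.1 lets the form go home and come back. That fits a form handed out at the hospital, and its stated purpose is independence of the answers.
- *Adverse events in non-attenders go unrecorded.* They are noted at each follow-up interval, which is not the same as each attended visit. Their loss is possible but not certain.
- *The 10-year result describes attenders only.* The SAP plans LOCF, and the full analysis set needs only one post-baseline assessment. Non-attenders are therefore included, with old scores. The 1.5 to 4.5 points apply to an observed-case mean.

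It is also fair to say that the 30% was set to secure the survival analysis and may include deaths and untraceable patients, who cannot return a form. A patient whose implant status is known by telephone may not be counted in it at all. Survival is the SAP's primary endpoint (5.1), and the telephone minimum protects it. Finally, SAP 7.4 states that the study was terminated early.

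All of this narrows the point without removing it. No provision obtains HOOS after a missed visit, and leaving it to the initiative of three sites invites inconsistent collection.

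**Conclusion.** The point holds as a gap in data collection, not as a contradiction in the plan. Implant status is the only minimum item named for telephone contact, no route to HOOS is given for non-attenders, and the default is a carried-forward score about five or more years old at the 10-year time point.

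At most about 67 of 225 patients are affected, if the 30% covers everyone without a 10-year visit. A reader might take all of them as recoverable; the documents do not support that, and the recoverable share is smaller and unknown. The observed-case error of up to 1.5 to 4.5 points, falling to about 0.6 to 1.9, depends on the assumed 5 to 15 point difference and on half of the non-attenders returning representative forms. The error of the planned LOCF analysis cannot be computed. The change is a worthwhile, low-cost improvement to a secondary endpoint and leaves the survival analysis as it is.

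**What to change.** - **Protocol 3.4:** for every patient who refuses or cannot attend but can be reached and still consents to contact, send the HOOS by post within the visit window, self-completed as in Protocol 3.1. On the call already planned, record reoperations and other complications since last contact, as well as implant status.
- **SAP 7.3:** state that a returned form is used as the observed value in place of LOCF. SAP 7.11 needs little change because it already summarises scores at all recorded time points.
- **Reporting:** give the numbers of observed and carried-forward HOOS values at 10 years, preferably with a summary that leaves out the carried-forward ones.

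The cost is postage, a few CRF fields and an amendment. The drawback is that a posted HOOS has no matching HHS or radiograph, so patient numbers will differ between endpoints. Because the study was terminated early, the collection change applies only where contact is still possible. The reporting change can be made regardless.

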3.5 Patient recruitment

Ethical approval is required according to the local regulations of the participating countries. Patients will be screened according to inclusion and exclusion criteria by the investigator. If inclusion criteria are met, patients will be informed about the observation accompanying the surgical procedure. Patients are enrolled in this observation only after they have given a written informed consent. The Patient enrolment has to be carried out within a period of 12 months.

4 DESCRIPTION OF THE DEVICES

4.1 Implants

In this study, the cementless POLARSTEM® will be used in combination with a well documented, cementless acetabular component from Smith & Nephew Orthopaedics AG.

4.2 Instruments

The participating surgeons will only use instruments supplied by Smith & Nephew Orthopaedics AG for the implantation of the POLARSTEM®. All instruments will be used conform to the instructions of the manufacturer.

5 ETHICAL AND LEGAL ASPECTS

5.1 Ethical aspects

This clinical trial will be performed in agreement with the “Declaration of Helsinki” (Version of 1994) and ISO 14155.

Participation in this study is voluntary and it is the patients’ right to stop the participation at any time without any declaration of reasons.

Patients will be informed orally and in written form about the study, its risks and benefits and their signed informed consent will be recorded.

5.2 Legal aspects

Approval from ethics committee is required prior any patient recruitment.

Patients’ name and other confidential information are subject to confidential medical communication and patients’ data will be made fully anonymous for analysis purposes.

For monitoring purposes (through notified bodies or the study monitors), it might be necessary to identify the patients’ name and to check original medical records to ensure proper study procedure. For this case the patient has given his signed informed consent.

6.3 Publication policy

The results of all study sites will be pooled regularly into an overall-publication and submitted to a peer-reviewed anglophone journal. The publication schedule will be defined by the group of investigators. The authorship is defined as follows:

[name]; [name]; [name]; [name], [name], [name], [name], [name]

Any change to this authorship requires mutual written agreement from the INVESTIGATORS

1 LIST OF ABBREVIATIONS

Abbreviation	Definition
AE	Adverse Event
CRF	Case Report Form
FAS	Full Analysis Set
HHS	Harris Hip Score
HOOS	Hip Disability and Osteoarthritic Outcome Score
LOCF	Last Observation Carried Forward
N (or n)	Total Sample Size (or subgroup sample size)
SAP	Statistical Analysis Plan
TFL	Table, Figure and Listing
WOMAC	Western Ontario and McMaster Universities Arthritis Index

CONFIDENTIAL AND PROPRIETARY

This document contains information that is confidential and proprietary to Smith & Nephew PLC and Smith & Nephew, Inc. and is intended for use only by Smith+Nephew and its manufacturer. It shall not be reproduced or copied in whole or in part, nor shall the contents be disclosed by any means without prior written permission from Smith+Nephew, nor shall anyone make any use of it that is contrary to the expressed or implied wishes of Smith+Nephew.

Statistical Analysis Plan

Multicenter Clinical Observation Using the Cementless Version of the POLARSTEM™

Number: D10070
ST: 1133
Version: 1.0, 30-Nov-2021
Page: 5 of 19

2 INTRODUCTION

The following Statistical Analysis Plan (SAP) details the statistical considerations, including the data analysis methods, for the Study Protocol D10070. Related documents to this SAP are the Study Protocol, Case Report Form (CRF), and Tables, Figures and Listings (TFL) Templates Shells.

The POLARSTEM™ is a commercially available cementless hydroxyapatite (HA) coated primary hip stem that has been in clinical use since 2002. The aim of this multicenter study is to validate the short-, mid- and long-term outcome of the POLARSTEM™ by evaluating standard efficacy and safety parameters. The preoperative status of the patients including demographic information, the surgical data, clinical and radiological outcomes will be documented.

3 STUDY DESIGN

The study is a prospective long-term multicenter clinical observation study. Overall a minimum of 225 patients were enrolled consecutively into the study at 3 sites. Patients enrolled into the study had at least one of the following indications:

- Primary or Secondary coxarthrosis
- Rheumatoid arthritis
- Developmental dysplasia of the hip
- Fracture or avascular necrosis of the femoral head

The patients were enrolled consecutively over 12 months and followed up for 10 years with observations at 3 months, 1 year, 3 years, 5 years and 10 years.

4 STUDY OBJECTIVES

The goal of this multicenter clinical observation study is to validate the short-, mid- and long-term outcome efficacy and safety of the POLARSTEM.

CONFIDENTIAL AND PROPRIETARY

This document contains information that is confidential and proprietary to Smith & Nephew PLC and Smith & Nephew, Inc. and is intended for use only by Smith+Nephew and its manufacturer. It shall not be reproduced or copied in whole or in part, nor shall the contents be disclosed by any means without prior written permission from Smith+Nephew, nor shall anyone make any use of it that is contrary to the expressed or implied wishes of Smith+Nephew.

Statistical Analysis Plan

Multicenter Clinical Observation Using the Cementless Version of the
POLARSTEM™

Number: D10070
ST: 1133
Version: 1.0, 30-Nov-2021
Page: 6 of 19

4.1 Primary Objective(s)

- Evaluation of function, range of motion (ROM), and pain as assessed by the Harris Hip Score (HHS), Hip disability and osteoarthritis outcome score (HOOS), an extension of the Western Ontario and McMaster Universities Osteoarthritis Index (WOMAC).
- Radiographic changes as defined by radiolucent lines, osteolysis, hypo- and hypertrophy implant loosening.

4.2 Secondary Objective(s)

- Intra- and perioperative implant-related “Adverse Events” (AE) and complications until discharge.
- Postoperative AE up to 10 years after the surgery

4.3 Exploratory Objective(s)

Not applicable.

CONFIDENTIAL AND PROPRIETARY

This document contains information that is confidential and proprietary to Smith & Nephew PLC and Smith & Nephew, Inc. and is intended for use only by Smith+Nephew and its manufacturer. It shall not be reproduced or copied in whole or in part, nor shall the contents be disclosed by any means without prior written permission from Smith+Nephew, nor shall anyone make any use of it that is contrary to the expressed or implied wishes of Smith+Nephew.

Statistical Analysis Plan

Multicenter Clinical Observation Using the Cementless Version of the POLARSTEM™

Number: D10070
ST: 1133
Version: 1.0, 30-Nov-2021
Page: 7 of 19

5 STUDY ENDPOINTS

5.1 Primary Endpoint

Short term, medium term and long term survival rates at 3 months and at 1, 3, 5, and 10 years.

5.2 Secondary Endpoints

- Harris Hip Score (HHS)
- HOOS Score (Hip Dysfunction and Osteoarthritis Outcome Score), which includes the complete WOMAC Osteoarthritis Index
- Radiological: radiolucent lines, osteolysis, hypo- and hypertrophy of the cortex, loosening of the implant or migration

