1 STUDY OBJECTIVES

1.1 Background

Total hip arthroplasty (THA) has been an established treatment procedure for patients suffering osteoarthritis of the hip and other joint diseases. However, THA alters the distribution of mechanical forces around the hip joint leading to bone remodeling related to implant design and mechanical properties as implied by Wolff's law. According to this law, an implantation of a femoral prosthesis induces a reduction of the proximal compressive stresses and a reactive loss of the proximal femoral bone mass. Although stress shielding has been described as clinically irrelevant with some stem designs (i.e., double-tapered form) [1], others suggest that this phenomena can compromise the implant stability and thus the clinical outcome of a THA and may predispose to loosening, migration as well as complications of the implant during revision [2, 3]. Furthermore, proximal radiolucent lines may provide wear particles (e.g., polyethylene) the possibility to migrate along the bone-implant interface, enlarging the risk of osteolytic processes [4].

Hydroxyapatite (HA) coatings have been widely used in THA due to their osseointegrative properties [5, 6]. HA on proximal stems have been shown to improve osseointegration, thus facilitating load transmission in the metaphysal part of the femur and hence reduced stress shielding. An improved osseointegration may also function as a barrier to migration of wear debris to the bone-implant interface, eventually leading to reduced osteolysis and increased implant long-term survival.

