1.3 Objectives

The goal of this multicenter clinical observation is to validate short-, mid-, and long-term outcome (efficacy and safety) of the POLARSTEM®.

Efficacy evaluations

- Evaluation of function, range of motion (ROM) and pain as assessed by Harris Hip Score, Hip disability and osteoarthritis outcome score (HOOS) [7, 8], an extension of the Western Ontario and McMaster Universities Osteoarthritis Index (WOMAC).
- Radiographic changes as defined by radiolucent lines, osteolysis, hypo- and hypertrophy, implant loosening or migration

Safety evaluations

- Intra- and perioperative device-related adverse events (AE) and complications up to discharge
- Postoperative AE up to 10 years

Long-term survivorship will be calculated according to Kaplan-Meier with stem revision due to any reason as endpoint.

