7.11 Analysis of Secondary Endpoints

- Harris Hip Score (HHS)

CONFIDENTIAL AND PROPRIETARY

This document contains information that is confidential and proprietary to Smith & Nephew PLC and Smith & Nephew, Inc. and is intended for use only by Smith+Nephew and its manufacturer. It shall not be reproduced or copied in whole or in part, nor shall the contents be disclosed by any means without prior written permission from Smith+Nephew, nor shall anyone make any use of it that is contrary to the expressed or implied wishes of Smith+Nephew.

Statistical Analysis Plan

Multicenter Clinical Observation Using the Cementless Version of the POLARSTEM™

Number: D10070
ST: 1133
Version: 1.0, 30-Nov-2021
Page: 17 of 19

- HOOS Score (Hip Dysfunction and Osteoarthritis Outcome Score), which includes the complete WOMAC Osteoarthritis Index
 - The different dimensions of and the overall HHS, and WOMAC from HOOS scores at all recorded time points and end of study will be summarized using mean, median, SD, minimum, and maximum. A paired sample t-test (or a non-parametric equivalent such as the Wilcoxon signed-rank test) will be used to test the difference between preoperative and postoperative scores.
- Radiological: At all recorded time points (from the perioperative through the 10 year postoperative follow-up), the following analyses would be carried out:
 - For general findings: At the acetabulum position, cranial migration (mm), medial migration (mm) and tilted angle would be summarized using descriptive characteristics for continuous variables; At the stem position, varus tilting, valgus tilting and sunken (mm) will be summarized using descriptive statistics for continuous variables; Integration in general/acetabulum, integration in general/stem and ectopic ossification will be summarized using descriptive statistics for categorical variables.
 - Within the cup and the stem (by zone): The number and percent of hips with osteolysis will be summarized; for seams (0mm, 1mm, 2mm &>2mm), atrophy (none, mild, moderate & severe) and hypertrophy (none, mild, moderate & severe) their frequencies (n) and percentages will be presented.

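### Loosening is a declared endpoint, but SAP 7.11 plans no loosening result, and its per-visit radiographic tables can understate loosening among revised stems

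*SAP*

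**What the plan says.** Loosening is declared in several places. Protocol 1.3 gives as an efficacy evaluation "Radiographic changes as defined by radiolucent lines, osteolysis, hypo- and hypertrophy, implant loosening or migration", and the protocol summary names it among the main parameters. SAP 4.1 puts "hypo- and hypertrophy implant loosening" inside a primary objective. SAP 5.2 makes "loosening of the implant or migration" part of a secondary endpoint.

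SAP 7.11 then lists the radiological analyses:
- Cup: cranial and medial migration and tilt angle.
- Stem: "At the stem position, varus tilting, valgus tilting and sunken (mm) will be summarized using descriptive statistics for continuous variables".
- General findings: "Integration in general/acetabulum, integration in general/stem and ectopic ossification will be summarized using descriptive statistics for categorical variables".
- By zone: "The number and percent of hips with osteolysis will be summarized", together with seams, atrophy and hypertrophy.

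Three other rules bear on a stem that is removed. Protocol 3.4 ends observation at explantation, and "the latest status will be recorded as an endpoint". SAP 7.3 treats data missing because of revision as device failure. The same section fills missing outcome values at scheduled visits by LOCF and makes no exception for revised hips or radiographic data.

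**The concern.** An endpoint that is declared but has no planned output may go unreported, or be defined only after the data have been seen. Loosening is also close to the reason for studying this stem. Protocol 1.1 cites the view that stress shielding "may predispose to loosening, migration as well as complications of the implant during revision", and presents the hydroxyapatite coating as a way to reduce stress shielding. The link from coating to loosening is indirect, but a reader will look for the result.

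Revision adds a second difficulty. A stem taken out for loosening has no later film. If its last film looked sound, a table built from films at each visit never records it as loose. Such tables could show little or no loosening at 10 years although some stems had been removed for it.

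**Working it through.** The documents give no loosening or revision counts, so there is no figure of the plan's own to reproduce on this point. The check is a comparison of text, followed by an illustration on assumed counts.

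**Endpoint against output.** None of the SAP 7.11 outputs is loosening. Tilting and sinking are summarised as continuous measurements, with no threshold that would make a stem loose. Integration is categorical, but its categories are not stated and nothing maps one of them to loosening. SAP 7.14 allows other CRF data to be summarised, but that is discretionary and does not amount to a planned analysis of a declared endpoint.

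**What happens to a revised stem.** Take a stem that looks sound at 3 years and is revised for loosening at year 4. Films are due at 3 months and 1, 3, 5 and 10 years (Protocol 3.3), so gaps of two and five years leave room for this.
1. Device failure (SAP 7.3) works in the survival analysis. It cannot be entered as a seam width, a zone code for osteolysis or millimetres of sinking.
2. LOCF (SAP 7.3) does yield a radiographic value, but it is the 3-year film of a stem no longer in the patient, shown as a 5- or 10-year finding.
3. If neither rule is applied to the films, the hip is absent from later tables.

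The SAP does not say which route applies. Routes 2 and 3 both miss the loosening if the last film was sound. If the last film already showed loosening, LOCF keeps it.

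**Illustration.** Inputs: 225 patients implanted (SAP 7.15); a target of 100 implants surviving 10 years and 30% drop-out (Protocol 2.2). Assumptions: one stem per patient; k stems revised for loosening, each after a sound last film; no loose stem among those still in place; either 100 or 157 hips with a 10-year film (225 × 0.70 = 157.5). Films alone then show 0.0% loose for every k. Counting the k stems as loose gives k/(100 + k), k/(157 + k) or k/225:

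| k | of 100 + k | of 157 + k | of 225 |
|---|---|---|---|
| 1 | 1/101 = 1.0% | 1/158 = 0.6% | 1/225 = 0.4% |
| 2 | 2/102 = 2.0% | 2/159 = 1.3% | 2/225 = 0.9% |
| 5 | 5/105 = 4.8% | 5/162 = 3.1% | 5/225 = 2.2% |
| 10 | 10/110 = 9.1% | 10/167 = 6.0% | 10/225 = 4.4% |

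The values of k are arbitrary. With k = 0 the difference is zero.

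**The case against.** The strongest reply is that these failures are not lost to the study. Protocol 1.3 makes stem revision for any reason the Kaplan-Meier event, and survival is the primary endpoint (SAP 5.1, 7.10). Revisions are tabulated or listed by type (SAP 7.10), and SAP 7.6 accounts for revisions by visit at hip level. All of this stands, so a reader who infers that the plan hides or discards failed stems would be wrong. It does not supply a loosening result, however. The survival event pools all reasons for revision, type of revision is not the reason for it, and the disposition tables are not linked to radiographic findings.

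A second reply is that the integration categories may record loosening in the CRF or table shells, which are not among the documents. That is possible. If so, the remedy for the definition is one sentence naming the category; the handling of revised stems would still be open.

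Two stronger inferences are tempting. One is that the 10-year radiographic picture is too favourable as a matter of fact. The documents do not support this: the handling of revised hips is unsettled, there may be no revisions for loosening, and a last film may already show it. The other is that adding the outcome can only worsen the reported figure. That depends on the denominator: 2 loose among 100 filmed hips is 2.0%, while the same 2 among 225 implanted stems is 0.9%.

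Finally, this is one component of a descriptive endpoint in a single-arm observational study, with no hypothesis on loosening. That limits the consequences but does not remove the gap.

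**Conclusion.** The point holds in a limited form. A declared endpoint has no definition and no planned result. For revised stems, the only rule that gives a radiographic value would report a film of a removed stem at a later visit. The per-visit tables can understate loosening when the last film before revision looked sound; the documents do not show that they do.

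The size cannot be determined. With one stem per patient, each stem revised for loosening after a sound last film is 1/225, about 0.4 percentage points. The primary survival analysis is not affected.

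**What to change.** In SAP 7.11:
- Add a hip-level stem loosening outcome: an investigator finding of loosening on any film (or the integration category that the CRF uses for it), or stem revision with loosening as the recorded reason. Check first that the CRF records a reason, since the SAP mentions only type of revision (7.10) and a binary revision indicator (7.4).
- Report the number of events and the cumulative incidence with 95% CI at 3 months and 1, 3, 5 and 10 years among implanted stems. Censor at last film or contact, and treat death and revision for other reasons as competing events (Aalen-Johansen estimator). SAP 7.4 says the study was terminated early, so a method that uses incomplete follow-up is preferable to a crude percentage.
- State, with a matching exception in SAP 7.3, that LOCF is not applied to radiographic findings after revision.
- Label the per-visit tables as hips still in place, and show the number revised before each visit; the SAP 7.6 accounting should provide most of this.
- Tabulate revisions by reason where recorded.

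The cost is SAP wording and one or two extra tables, with no new data collection if the CRF holds the reason for revision. The downside for the sponsor is a possibly less favourable loosening figure.
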